#### 6.1.2 ACQUISITION

The brand new Sklip dermatoscope devices used in this Study will be shipped by the Study Sponsor to the OHSU Department of Dermatology in order to prepare, sanitize, and ensure all materials are packaged prior to sending to Participants. The devices will be provided on a rolling basis for enrolled Participants enrolled for a targeted goal of 310 total devices used. The Sklip dermatoscope device and access to the SMSA will be provided at no cost to all Study Participants. The OHSU Department of Dermatology will offer shipping to Study Participants at other Study Sites. Costs for shipping will be covered by the Study Sponsor.

#### 6.1.3 FORMULATION, APPEARANCE, PACKAGING AND LABELING

The description of the proposed device, indications for use, manufacturing process, device storage, handling, accountability, and access (limited to appropriate personnel and only by appropriate Study subjects) are provided in this document above in *Section 6.1.1 Study Intervention Description*. The device has been granted FDA Breakthrough Designation record number Q211049. Sklip System instructions for use that include safety instructions and warnings are included in the devices sent out to Study Participants.

1. *Sklip dermatoscope device hardware* is currently registered as a Class 1 Medical Device with the FDA.
2. *Sklip Mole Scanning Algorithm (SMSA)* has been evaluated by the FDA and received FDA Breakthrough Designation. The intended use for the Sklip System is a stand-alone triage tool (FDA Class 2). The Sklip System is not intended for diagnostic use (FDA Class 3)

#### 6.1.4 PRODUCT STORAGE AND STABILITY

The SMSA will be available to Participants for research use only using a dedicated username and password on a non-commercial version of the Sklip App. Use of the Sklip System is completely anonymous. Sklip dermatoscope device storage will be on the CHH1 14th floor in a secure location dedicated to the Department of Dermatology.

#### 6.1.5 COMPATIBILITY

Not applicable. Our Study does not involve any drug or therapeutic agent.

## 6.1.6 HANDLING

Access to Sklip dermatoscope devices will be limited to appropriate personnel within the OHSU Department of Dermatology and other Study Sites. Access to the non-commercial version of Sklip app for the purpose of research will be limited to enrolled Study Participants. OHSU dedicated employees will have access to the master list to match patient MRN to the anonymous username for the purpose of this Study. An OHSU Study team member will provide usernames and passwords to the additional Study Sites. Since this Study is anonymous the Sponsor will not receive any patient health information (PHI) during this Study. All Sklip dermatoscope devices will be sent one way to Participants via USPS or UPS.

## 6.1.7 PREPARATION

Once a Participant is officially enrolled in the Study, a designated Study Coordinator will properly sanitize and prepare a package of the necessary materials the Participant will need for the Study. The following are items that will be prepared to be shipped to the Participant via USPS or UPS:

- Instructions for Participants
- One (1) printed Participant Mole Log Sheet
- One (1) Sklip dermatoscope device (charging cable and dermoscopy oil)
- One (1) username/password enabling SMSA access using the Sklip App

## 6.1.8 ADMINISTRATION

- 1) All necessary materials will be shipped to all Participants via USPS or UPS as described in 6.1.7 PREPARATION.
- 2) Study Coordinators will provide specific onboarding training:
  - a. The Participants will be trained on how to log their SSE self-selected PSLCs in their Participant Mole Log Sheet. They will also be asked to submit a copy of their Participant Mole Log Sheet using nPhase REDCap image upload, or email ([[contact]](mailto:[contact])). Participants will be reminded to bring it in person during their in-person visit.
  - b. The Participants will be informed on the requirement to follow up in-person for a FBSE with a Study Site dermatology Provider within 28 days of completing the At-home Phase.
  - c. The Participant will be informed that all costs associated with normal medical care activities will not be covered by the Study Sponsor as described in the sections above.

At the end of the Study, the Participants will be sent an nPhase REDCap Cloud survey that will document Participant responses to the number of self-selected PSLCs and the number of suspicious PSLCs identified by the dermatology Provider during the Study.

## 6.1.9 SPECIAL CONSIDERATIONS FOR ADMINISTRATION

N/A

## 6.1.10 ACCOUNTABILITY

The Investigators, or a responsible party designated by the Investigators, will maintain a careful record of the inventory and disposition of the Study agent.

Responsibility for device accountability at Study Sites rests with its Investigator; however, the Investigator may assign some of the device accountability duties to an appropriate designee. Inventory and accountability records

will be maintained and readily available for inspection by the Study monitor and are open to inspection at any time by any applicable regulatory authorities or other oversight bodies.

The Investigator or designee will collect and retain all used, unused, and partially used containers of the Study device or devices unwanted by Participant at the end of the Study until full accounting has been completed. The Investigator or designee will maintain records that document:

- Investigational product delivery to the Study Site.
- The inventory at the Site.
- Number of investigational products shipped to Participant and date of shipment
- Any return of investigational product to the Investigator or designee.

These records will include dates, quantities, and the unique code numbers assigned to the investigational product and Study Participants.

The investigational product must be used only in accordance with the protocol. The Investigator will also maintain records adequately documenting that the Participants were provided the correct Study materials specified based off the Participants randomly assigned group. Completed accountability records will be archived by the Site.

#### 6.1.11 DESTRUCTION AND RETURN

At the completion of the Study, the Investigator or designee will oversee repurposing or redistribution of any remaining Study product to be used in other applicable studies. There is no indication for destruction of unused Study devices.

### 6.2 DEVICE-SPECIFIC CONSIDERATIONS

#### Device Description

Please refer to 6.1.1 (Device Description)

## 7. TREATMENT PLAN

### 7.1 DOSAGE AND ADMINISTRATION

N/A

#### 7.1.1 DEFINITION OF DOSE-LIMITING TOXICITY (DLT)

N/A

#### 7.1.2 DEFINITION OF MAXIMUM TOLERATED DOSE (MTD)

N/A

#### 7.1.3 DOSE DELAYS

N/A

#### 7.1.4 DOSE ESCALATION

N/A

**7.1.5 DOSE DE-ESCALATION**

N/A

**7.1.6 GENERAL DOSE MODIFICATION GUIDELINES**

N/A

**7.2 DISCONTINUATION FROM STUDY INTERVENTION**

Discontinuation from the Study intervention (reported discontinued use of Sklip System by Participants) does not mean discontinuation from the Study, and remaining Study procedures (nPhase REDCap Cloud survey, chart reviews) should be completed as indicated by the Study protocol.

The data to be collected at the time of Study intervention discontinuation will include the following:

- a) Anonymous Sklip App analytics per Study Participant (frequency of use)
- b) Data obtained from chart reviews to track the number of submitted PSLCs, the number of PSLCs identified as SUSPICIOUS by the dermatology Provider during the in-person FBSE, the chosen method of follow-up, and any relevant pathology results for each Participant.
- c) Data from the end of Study REDCap Cloud survey.

Participants MUST discontinue investigational product for any of the following reasons:

- Participant's request to stop Study intervention. Participants who request to discontinue using the provided Sklip System will remain in the Study and must continue to be followed for protocol specified follow-up procedures. The only exception to this is when a Participant specifically withdraws consent for any further contact (refer to Section 5.2)
- Loss of ability to freely provide consent through imprisonment, or involuntarily incarceration for treatment of either a psychiatric or physical (e.g., infectious disease) illness.

All Participants who discontinue Study intervention should comply with protocol specified follow-up procedures as outlined in Section 8. If Study intervention is discontinued prior to the Participant's completion of the Study, the reason for the discontinuation must be documented in the Participant's medical records and entered on the appropriate CRF.

**7.3 TREATMENT PERIOD AND MAINTENANCE**

Interventional treatment will not be provided in this Study. All treatment and management for Participants will follow standard OHSU clinical care protocol.

**7.4 CONCOMITANT MEDICATION AND SUPPORTIVE CARE GUIDELINES**

N/A

**7.5 PRECAUTIONARY MEDICATIONS, TREATMENTS, AND PROCEDURES**

N/A

**7.6 PROHIBITED MEDICATIONS, TREATMENTS, AND PROCEDURES**

There are no restrictions on specific medications, treatments, or procedures for this study.

## 7.7 OTHER TREATMENT MODALITIES

N/A

## 8. STUDY PROCEDURES/EVALUATIONS AND SCHEDULE

### 8.1 STUDY-SPECIFIC PROCEDURES

#### 8.1.1 MEDICAL HISTORY

The Participant's medical history will be obtained from their medical records. Relevant medical history for this Study include:

- Demographic information (age, gender, race, location of residence)
- History of melanoma skin cancer confirmed by pathology report
- History of non-melanoma skin cancer confirmed by pathology report
- Whether the Participant has had a virtual communication (MyChart encounter, virtual video visit, direct message, e-visit) or in-person visit with a dermatology Provider within the last 90 days.

#### 8.1.2 DISEASE ASSESSMENT

All Participants will be required to obtain an in-person FBSE. Since PSLCs will be evaluated per standard clinical care pathways, the evaluating dermatology Provider may or may not be involved in the Study. The dermatology Provider will be blinded to Participant activity, including the Participant Mole Log Sheet. The dermatology Provider may choose to perform biopsy, when applicable, independent of Participant at-home findings.

Biopsies may be performed for suspicious lesions identified by the dermatology Provider during the FBSE and will be assessed by histologic assessment as part of current standards of care for diagnosis, independent of the Study. **The use of the Sklip System is for triage only and is not intended to act as a substitute for official diagnosis via pathology results, and all subsequent management and treatment of disease will be based off official histologic diagnosis and in accordance current guidelines.**

#### 8.1.3 MEDICATION REVIEW

N/A

#### 8.1.4 PHYSICAL EXAMINATION

In-person Phase activity is described in Section 3.1 above.

#### 8.1.5 RADIOGRAPHIC OR OTHER IMAGING ASSESSMENTS

Not applicable. All Participant-identified suspicious lesions that require further evaluation will be assessed with digital dermoscopy.

#### 8.1.6 ADVERSE EVENT EVALUATION

The device does not pose a serious risk to the health, safety, or welfare of subjects. The clinical trial design is such that the potential risk of not flagging a suspicious lesion is appropriately mitigated and the trial itself does not pose a potential for serious risk to the health, safety, or welfare of a subject.

### 8.1.7 COUNSELING PROCEDURES

The results of this Study will not be made available to Participants. Participants will receive direct dermatology Provider care after visit summaries and biopsy results, when applicable, as part of standard of care according to their individual case.

### 8.1.8 ASSESSMENT OF STUDY AGENT ADHERENCE

Participants are not required to adhere to the interventional product. Frequency of use of the Study agent is measured and recorded (via Sklip analytics or nPhase REDCap Cloud survey), however use of the Study intervention is voluntary and at the discretion of the Participant.

### 8.1.9 ASSESSMENT OF PARTICIPANT-REPORTED OUTCOMES

Study Coordinators will provide specific onboarding training for all Participants on how to record each self-selected PSLC in their Participant Mole Log Sheet. Participants will be asked to record this information and self-report it at the end of the Study in the nPhase REDCap Cloud survey.

## 8.2 LABORATORY PROCEDURES AND EVALUATIONS

### 8.2.1 PREGNANCY TEST

N/A

### 8.3 BIOMARKER, CORRELATIVE, AND SPECIAL STUDIES

N/A

#### 8.3.1 LABORATORY CORRELATIVE STUDIES

N/A

#### 8.3.2 SPECIAL STUDIES

N/A

## 8.4 SCREENING ASSESSMENTS

Screening will be done once during the initial contact by a Study Coordinator to have informed consent explained and signed. Since the eligibility criteria measurements are unlikely to change (of age, English speaking, access to smartphone, etc.) during the Study, only an initial baseline screening is required.

## 8.5 BASELINE ASSESSMENTS

After confirming whether the Participant meets the eligibility criteria, no further baseline screening or assessment is necessary to obtain prior to beginning the Study.

## 8.6 ASSESSMENTS DURING TREATMENT

Not applicable. There is no interventional treatment or therapies in this Study. The number of submitted PSLCs, the number of PSLCs qualified for follow-up, the chosen method of follow-up, and any relevant pathology results for each Participant will be recorded and analyzed as part of period retrospective chart reviews conducted by a Study Coordinator as described in Sections above.

## 8.7     **EARLY TERMINATION OR END OF TREATMENT VISIT**

EARLY TERMINATION – N/A; PARTICIPANTS DO NOT HAVE A PHYSICAL STUDY VISIT

END OF TREATMENT – N/A

## 8.8     **FOLLOW-UP**

There will be no scheduled follow-up after completion of the Study. Any follow up for Participants after conclusion of the 42 day Study will be part of the Participant's standard clinical care pathways and not the responsibility of Study Coordinators or the Study Sponsor.

## 8.9     **UNSCHEDULED VISITS**

All Participants will be requested to engage in an in-person visit at their Study Site within 28 days of completing the at-home Phase to obtain a FBSE. If the Participant does not already have a scheduled visit, Study Site dermatology providers will agree to accommodate overbookings to ensure that each participant can obtain an in-person visit within the

## 8.10    **SCHEDULE OF EVENTS**

**Table 3. Schedule of events**

Days ( $\pm 3$ Days)	Recruitment	Enrollment	Data Entry	Phase 1 Survey
	Days -28 to -1	Day 1	Continuously	Day 42
Invite Participants	X			
Screening, Inclusion/exclusion criteria	X			
Informed Consent	X	X		
Onboard training		X		
MyChart, Direct message, Calls, Email, or Text	X	X		X
EMR Chart Review			X	X
Participant nPhase REDCap Cloud Survey	X	X		X

## 9. EFFICACY MEASURES

Assessment of any Participant self-selected PSLCs as part of the intervention in this Study will be conducted by the Sklip System. The Sklip System incorporates proprietary artificial intelligence (Ai) DDI analysis (SMSA) of PSLCs based on a modified dermoscopy Three-Point Checklist (MD3PC). PSLs presented to the SMSA are triaged into three categories: UNREMARKABLE, SUSPICIOUS or ERROR, and its performance has been verified and validated in alignment with expectations necessary for the safety and effectiveness of the device aligned with its intended use.

### 9.1 DEFINITION OF EFFICACY MEASURES

**Measurable disease:** Measurable PSLCs are defined as those that can be accurately measured in at least one dimension as > 3 mm diameter by naked-eye examination and confirmed using a medical ruler or professional dermatoscope (i.e. Heine D30) with a fixed measurement ruler in the field of view. There is no therapy introduced or evaluated in this Study, therefore parameters for determining disease response are unnecessary.

### 9.2 DISEASE EVALUATION

Any suspicious skin lesions (including PSLCs) that get further evaluated in this Study will be via Study Site normal clinical care pathways. Per current guidelines, all definitive diagnosis of dermatology Provider verified suspicious skin lesions with concern for malignancy must be made via biopsy and histologic assessment by the Study Site.

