**Schedule for data collection:**

In order to avoid Participant PSLC recollection-bias, Study Coordinators will use the Participant Mole Log Sheet (PMLS) and Participant taken SCI/DDI for guidance and **record** the following Datasets in REDCap Cloud:

- A) Total number of PSLCs identified by the Participant at-home
- B) Total number of PSLCs identified by the DP in-office
- C) One (1) individual SMSA output recorded in the PMLS, per target PSLC (SUSPICIOUS, UNREMARKABLE and ERROR)

Ensuring that no PHI is shared, Study Coordinators will **export** the following from the Participant smartphone/tablet gallery titled “Moles” to the Study Site smartphone/tablet gallery via Bluetooth or secure email:

- D) One (1) Participant-taken SCI, per target PSLC
- E) One (1) Participant-taken DDI, per target PSLC
- F) One (1) Participant-taken SMSA output screenshot, per target PSLC

Then, Study Coordinators will **acquire** and **export** the following from the Study Site smartphone/tablet gallery to an OHSU secure cloud storage service:

- G) One (1) Study Coordinator-taken DDI (near-perfect image technical quality) for each PSLC recorded in the PMLS and suspicious PSLCs identified by the DP in-office that were not recorded in the PMLS

Then, Study Coordinators will **upload** the DDI in Dataset (G) to the SMSA on a Study Site smartphone/tablet and **record** the following Datasets into REDCap Cloud:

- H) One (1) Study Coordinator-taken SMSA output for each PSLC, recorded in the PMLS, using Dataset (G) (SUSPICIOUS, UNREMARKABLE and ERROR), including one (1) screenshots

Then, the Study Coordinator will **record** the following Datasets into REDCap Cloud:

- I) All other SCI of suspicious PSLCs identified by the DP in-office that were not recorded in the PMLS
- J) All other DDI of suspicious PSLCs identified by the DP in-office that were not recorded in the PMLS
- K) Pathology reports for all PSLCs that were biopsied during the In-Person Phase
- L) Number of adverse events reported during the Study

-----End of In-person Phase-----

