**Description of Satellite Study required activities**

Satellite Study Sites will also complete the above activities and securely **submit** their Datasets (A-L) to the Lead Study Site via OHSU secure cloud storage services. The Lead Study Site will prepare individual Qualtrics surveys using images from the Datasets above to create the following Datasets:

Dataset M) SCI triage decision (SCI-TD) based on Datasets (D) and (I), when at least two of three expert dermatologist readers have a concordant triage decision (MONITOR or BIOPSY). If there is a lack of concordance, an internationally recognized dermoscopy expert (dermatologist) will act as a fourth reader to determine the final SCI-TD

Dataset N) DDI dermoscopic diagnosis ground truth (DDI-GT) for PSLCs that were not biopsied during the In-Person Phase, using images available in Datasets (E) and (J), when at least two of three expert dermatologist readers have a concordant dermoscopic diagnosis. If there is a lack of concordance, an internationally recognized dermoscopy expert (dermatologist) will act as a fourth reader to determine the final DDI-GT

Dataset O) Histologic diagnosis ground truth (H-GT) for lesions that were biopsied during the In-Person Phase, based on evaluations using either physical or digital histologic slides (described in Sections below), when both independent expert dermatopathologists have a concordant histologic diagnosis. If there is a lack of concordance, a third internationally recognized expert dermatopathologist will determine the final H-GT.

The Study Sponsor will be responsible for Study costs (logistics, shipping, handling, research reading fees) associated with the use of either physical or digital histologic slides to create Dataset O. If digital histologic images (DHI) are chosen, the Lead Study Site will be asked to prepare DHI for their own Study Site Participants who received a biopsy during the In-person Phase. The Lead Study Site will have the option to prepare DHI for the Satellite Study Sites.

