#### 11.4.2 ANALYSIS OF PRIMARY ENDPOINT(S)

For the Primary Endpoints, the SMSA outputs of “SUSPICIOUS” or “UNREMARKABLE” from Participant-taken DDI will be compared to the Ground Truth, described in the Sections above. For **Melanoma and atypical melanocytic nevi with uncertain malignant potential** (moderate, severe, and high grade atypia; those with pathology reports that include notes such as: borderline, cannot exclude melanoma, cannot exclude early evolving melanoma, unusual features, atypical spitz nevi, suspicion for melanoma, re-excision (or further removal) should be considered or is recommended in the pathologist management comment), a 2x2 table consisting of the following counts (number of PSLCs):

- True Positives (TP): the SMSA output of SUSPICIOUS agrees with the Ground Truth for PSLCs that were

biopsied and were diagnosed as Melanoma or atypical melanocytic nevi with uncertain malignant potential, using Dataset (O) (Histologic diagnosis ground truth (H-GT)),

- False Positives (FP): the SMSA output of SUSPICIOUS does not agree with the benign Ground Truth using Dataset (N) (DDI dermoscopic diagnosis ground truth) and Dataset (O)
- False Negatives (FN): the SMSA output of UNREMARKABLE does not agree with the Ground Truth for PSLCs that were biopsied and diagnosed as Melanoma or atypical melanocytic nevi with uncertain malignant potential using Dataset (O)
- True Negatives (TN): the SMSA output of UNREMARKABLE agrees with the benign Ground Truth, using both Dataset (N) and Dataset (O)

For **Melanoma and atypical melanocytic nevi with uncertain malignant potential**, Sensitivity ( $TP \div (TP + FN)$ ) of the Sklip System will be calculated with a lower one-sided 95% confidence interval using the Exact (Clopper-Pearson) method. For **Squamous cell carcinoma** and for **Basal cell carcinoma**, Sensitivity and lower one-sided confidence intervals will be estimated in the same manner as for Melanoma and atypical melanocytic nevi with uncertain malignant potential.

Specificity ( $TN \div (FP + TN)$ ) will be the same for Melanoma and atypical melanocytic nevi with uncertain malignant potential, SCC, and BCC, where:

- False Positives (FP): the SMSA output of SUSPICIOUS does not agree with the benign Ground Truth, using Dataset (N) and Dataset (O)
- True Negatives (TN): the SMSA output of UNREMARKABLE agrees with the benign Ground Truth, using Dataset (N) and Dataset (O)

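### A logged lesion that the provider marked suspicious, that was not biopsied and that the image panel reads as benign can only be scored FP or TN, and no planned analysis shows the effect

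*Combined protocol and SAP*

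**What the plan says.** Section 2.1 puts every lesion on the Participant Mole Log Sheet into the primary 2x2 table. The reference standard has two sources, set out in Section 3.1. Dataset O is expert histology for lesions biopsied in the In-person Phase. Dataset N is a dermoscopic image read "for PSLCs that were not biopsied during the In-Person Phase, using images available in Datasets (E) and (J"), settled "when at least two of three expert dermatologist readers have a concordant dermoscopic diagnosis" and otherwise by a fourth reader.

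Section 11.4.2 does not use the two sources symmetrically. TP and FN require a biopsy and a Dataset O diagnosis. FP and TN accept a benign result from either source; the TN entry reads "True Negatives (TN): the SMSA output of UNREMARKABLE agrees with the benign Ground Truth, using both Dataset (N) and Dataset (O").

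Biopsy itself is a clinical decision. Section 8.1.2 says "Biopsies may be performed for suspicious lesions identified by the dermatology Provider during the FBSE" and "The dermatology Provider may choose to perform biopsy, when applicable, independent of Participant at-home findings". Section 9.2 says "all definitive diagnosis of dermatology Provider verified suspicious skin lesions with concern for malignancy must be made via biopsy and histologic assessment". Dataset J, one of the inputs to Dataset N, is "All other DDI of suspicious PSLCs identified by the DP in-office that were not recorded in the PMLS", so the plan foresees provider-suspicious lesions without histology.

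Section 8.8 schedules no follow-up. Sections 3.1 and 3.2 allow a short review of medical records after the study phases, but Dataset O is limited to In-person Phase biopsies and no rule reclassifies a lesion from that review. The only additional analyses, in Section 11.4.6, are by skin type and by site.

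**The concern.** The lesions at issue carry three facts together: the participant logged them, a provider blinded to the at-home results judged them suspicious in person, and no histology exists. The provider's judgment is evidence that does not depend on the participant's image. The table makes no use of it. The panel, for a logged lesion, reads Dataset E, the participant-taken image source that SMSA also scores, so a poor image could mislead panel and device in the same direction.

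If the panel is wrong and the lesion is malignant, it cannot appear in the sensitivity denominator at all. It sits among the negatives, and whether that flatters or penalises the device depends on the SMSA output. The stake is mainly the 95% sensitivity goal for melanoma and atypical nevi, which rests on few positives.

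The class may also be hard to reconstruct later. Datasets A to L hold the provider's total count (B) and the provider-suspicious lesions missing from the log (I, J). None lists the provider's mark lesion by lesion for logged lesions.

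**Working it through.** **1. Where such a lesion lands (Section 11.4.2).** Take a logged, provider-SUSPICIOUS, unbiopsied lesion that the panel reads as benign.

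| SMSA output | Cell assigned | Cell if truly malignant | Effect of the error |
|---|---|---|---|
| UNREMARKABLE | TN | FN | sensitivity and specificity too high |
| SUSPICIOUS | FP | TP | sensitivity and specificity too low |

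**2. Plan figures reproduced (Section 11.2).** Formula (1): 1.96² × 0.974 × 0.026 / (0.10² × 0.023) = 422.98, stated as 423 lesions. Participants: 423 / 1.5 × 1.10 = 310.2, stated as 310.

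**3. Expected counts (Table 6).** Melanoma 10 plus atypical nevi 21 gives 31 positives. At the 97.4% sensitivity given in the Synopsis for this combined group, 31 × 0.974 = 30.2, so 30/31. (Table 6 itself places only 9 + 14 = 23 of the 31 in its suspicious row; 30/31 follows the stated sensitivity, not that row.) Lesions negative for malignancy: 220, of which 107 are non-suspicious, so specificity is 107/220 = 48.6%.

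**4. Hidden UNREMARKABLE cancers.** Let m such lesions be malignant; m is an assumption, as the documents give no number. Sensitivity becomes 30/(31 + m) and specificity (107 − m)/(220 − m). The bound is the planned lower one-sided 95% Clopper-Pearson limit.

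| m | Sensitivity | Lower bound | Specificity |
|---|---|---|---|
| 0 | 30/31 = 96.8% | 85.6% | 48.6% |
| 1 | 30/32 = 93.8% | 81.6% | 106/219 = 48.4% |
| 2 | 30/33 = 90.9% | 78.1% | 105/218 = 48.2% |
| 4 | 30/35 = 85.7% | 72.3% | 103/216 = 47.7% |

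Starting from 31/31 (100%, bound 90.8%), m = 1 gives 31/32 = 96.9% (86.0%) and m = 2 gives 31/33 = 93.9% (82.1%). One lesion is 1/107 = 0.9% of the expected non-suspicious negatives.

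**5. Hidden SUSPICIOUS cancers.** One such lesion should move from FP to TP: 30/31 becomes 31/32 = 96.9%, the bound goes from 85.6% to 86.0%, and specificity goes from 107/220 = 48.6% to 107/219 = 48.9%.

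**6. Break-even mix.** Sensitivity is unchanged in expectation if hidden cancers split at the device's own rate, 0.974/0.026 = about 37 SUSPICIOUS for each UNREMARKABLE one.

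**7. The 80% goals.** Table 6 expects 52 and 121 lesions in the two carcinoma groups. (Section 11.2's text and its tables attach the 12.5% and 29.2% prevalences to opposite carcinomas, so the groups are identified here by size.) At the tables' 95% sensitivity these give 49/52 and 115/121. The point estimate first falls below 80% at 10 hidden UNREMARKABLE lesions (49/62 = 79.0%) and at 23 (115/144 = 79.9%).

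**The case against.** **Section 9.2 is about care, not the research reference.** A reader might infer that the plan breaks its own rule by scoring such lesions from an image. The documents do not support that. Section 9.2 refers to normal care pathways, current guidelines and assessment by the Study Site. It can be read as saying that a definitive clinical diagnosis, where one is made, comes from histology. The research ground truth is defined separately and read by independent experts. What remains is a tension in wording between 9.2, 8.1.2 and Dataset N. The asymmetry in 11.4.2 does not depend on it.

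**The composite reference is deliberate.** It is said to have been discussed with the FDA, and the lesion is called benign only after a consensus read. Both points stand. Neither shows that this subgroup was considered.

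**Dataset J is outside the primary table.** Correct: J lesions are not in the log. J shows only that unbiopsied suspicious lesions are expected. The lesions affected here are those marked by both participant and provider.

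**The bias has two directions.** A reader might infer that sensitivity and specificity must both be too high. That holds only for the UNREMARKABLE part. Because the provider is blinded to the SMSA result, the biopsy decision is not driven by it, and a mix near step 6 would leave expected sensitivity unchanged. Lesions that the panel reads as benign from the same image source may lean UNREMARKABLE, but the documents neither establish nor bound this.

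**One lesion deciding the trial.** A reader might infer that a single hidden cancer turns success into failure. That is so only if the point estimate is the criterion. Section 11.4.2 plans a lower bound without saying which must reach the goal, and with 31 positives the bound cannot reach 95% even with none missed.

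**Conclusion.** The point holds as a gap in the analysis plan. Provider-SUSPICIOUS, unbiopsied, panel-benign lesions can enter only the negative side of the primary table, no planned analysis shows what that does, and the listed datasets may not allow the class to be identified afterwards.

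The sensitivity effect is about 3 percentage points on the melanoma and atypical-nevus point estimate per hidden UNREMARKABLE cancer near 30/31 (96.8% to 93.8%), and about 4 points on the exact bound. Specificity moves about 0.2 points per lesion in either direction. The 80% goals are little affected as point estimates.

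This rests on the Table 6 counts, on the 97.4% sensitivity, and on an assumed number of hidden cancers. How many lesions fall in the class, how many are malignant, and how they split by SMSA output are not in the documents. The documents therefore do not show that the primary estimates are biased upward overall, or that Section 9.2 strictly contradicts the ground truth. They do show that the question could not be answered from the analyses planned.

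**What to change.** Keep the composite ground truth as primary, and make these additions.

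- **Data capture:** record in REDCap, for each logged lesion, whether the provider marked it SUSPICIOUS. The plus sign that Section 3.1 already has drawn on the skin supplies this.
- **Reporting:** give the number of provider-SUSPICIOUS, unbiopsied logged lesions by SMSA output and panel read. This also exposes unbiopsied lesions that the panel reads as malignant, which have no cell in the 11.4.2 table.
- **Sensitivity analysis, pre-specified in 11.4.2:** (a) exclude the class; (b) bound sensitivity and specificity, counting the UNREMARKABLE lesions as FN at the lower extreme and the SUSPICIOUS lesions as TP at the upper extreme, for each disease goal in turn; (c) give the tipping count, that is, how many UNREMARKABLE lesions would have to be malignant for each goal to be missed, stating whether the point estimate or the bound is judged.
- **Wording:** reconcile Section 9.2 with Section 8.1.2 and Dataset N. No view is taken on clinical care, and no additional biopsy is proposed.

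The cost is one REDCap field, one table and a few lines of analysis text. The exclusion analysis has a limit: it removes negatives that may be the hardest for the device, so its specificity may move either way. For that reason it should support the primary analysis, not replace it.
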